### 5.1. Sample Size

Approximately 1200 patients with RMS will be randomized in this study (approximately 400 per treatment group). The primary analyses will compare the ARRs in each of the RPC1063 groups to the IFN  $\beta$ -1a group using a Poisson regression model at the alpha = 0.025 level. The control ARR is assumed to be equal to 0.3 (Mikol, 2008). Assuming extra-Poisson variation ( $\sigma^2$ =1.3) (Polman, 2011) and at least 12 months of follow-up per patient, the method of Nicholas (Nicholas, 2011) results in a total sample size of 1059 patients (353 per arm) in order to provide 80% power to detect a 43% reduction in the ARR (i.e., an ARR of 0.17 for RPC1063). To account for an assumed dropout rate of approximately 12%, approximately 1200 patients (400 per treatment group) will be enrolled.

## 5.2. Randomization, Stratification, and Blinding

Patients will be randomized 1:1:1 to receive IFN  $\beta$ -1a 30  $\mu$ g QW, RPC1063 0.5 mg QD, or RPC1063 1 mg QD. The randomization will be stratified by Baseline EDSS category ( $\leq$  3.5, > 3.5) and country.

The randomization will be based on a stratified blocked algorithm and will be done centrally by using an Interactive Voice Response System (IVRS).

A "dual assessor" approach will be used to evaluate efficacy and safety to prevent potential unblinding as result of observed efficacy, adverse events (AEs), or laboratory changes. Separate treating and examining investigators will be designated at each center prior to randomization. Patients will be instructed to not disclose symptoms related to their treatment regimen to the blinded evaluator (examining investigator). The blinded evaluator should communicate with patients only as needed to complete the neurological examinations.

In the event that the blinding needs to be broken because of a medical emergency, the Medical Monitor should be contacted immediately. The treatment assignment will be unblinded through the IVRS. Reasons for treatment unblinding must be clearly explained and justified in the eCRF. The date on which the code was broken together with the identity of the person responsible must also be documented.

## 5.3. Analysis Populations

### 5.3.1. Intent-to-Treat (ITT) Population

The ITT population will include all randomized patients who are confirmed to have received at least one dose of study drug. This will be the primary population for the analysis of all efficacy endpoints. All patients in the ITT sample will be analyzed

according to the treatment they were randomized to receive and not according to what they actually received, if different.

### 5.3.2. Per-Protocol (PP) Population

The PP population will be a subset from the ITT population with high treatment compliance and without any major protocol deviations. Major protocol deviations will include one or more of the following categories: major inclusion/exclusion criteria violations, poor study drug compliance, and other. The criteria for exclusion from the PP population will include, but are not limited to, those listed below:

- Violation of any of the following three inclusion criteria related to MS specific disease activity:
  - Must have a confirmed diagnosis of MS by the revised 2010 McDonald criteria
  - Must have a Baseline EDSS score between 0 and 5.0
  - Must have at least 1 documented relapse within the last 12 months prior to screening, OR, if at least 1 documented relapse occurred within the last 24 months prior to screening, evidence of at least 1 GdE lesion on brain MRI within the last 12 months prior to randomization
- Poor study drug compliance: compliance up to last dose of study drug <80% The PP population will be fully identified and documented prior to database lock.

#### **5.3.3.** Safety Population

The Safety population will include all patients who have received at least one dose of study drug. All patients in the Safety population will be analyzed according to the highest dose of RPC1063 treatment actually received (up to 1 mg) and not according to the treatment they are randomized to receive, in the event there is a discrepancy.

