#### Part B

In Part B, patients will be randomized 1:1:1 to receive one of the following 3 regimens:

- IFN β-1a 30 µg IM injection weekly for 24 months
- 0.5 mg RPC1063 oral capsule daily for 24 months
- 1 mg RPC1063 oral capsule daily for 24 months

Dosing will begin following randomization on Day 1.

Part B will be use a double-dummy design. Thus, patients randomized to RPC1063 0.5 or 1 mg will also receive weekly matching placebo IM injections and patients randomized to IFN  $\beta$ -1a 30  $\mu$ g will also receive daily matching placebo oral capsules.

For all patients in Part B, initial study treatment will consist of a 7-day dose titration regimen as shown in Table 7: for patients randomized to receive treatment with RPC1063, this regimen will consist of 0.25 mg RPC1063 starting on Day 1 for 4 days, and 0.5 mg RPC1063 starting on Day 5 for 3 days. All patients will be dosed with their assigned RPC1063 treatment level beginning on Day 8. Patients randomized to IFN  $\beta$ -1a 30  $\mu$ g will receive RPC1063-matching placebo titration kits.

Table 7 Titration Schedule for the RPC1063 Treatment Groups in Part B

	RPC1063/IFN β-1a dose (# RPC1063/Placebo capsules)							
Assigned treatment	Day 1	Days 2 to 4	Days 5 to 7	Day 8*				
RPC1063 0.5 mg	0.25 mg RPC1063 (1 x 0.25 mg capsule) + Placebo	0.25 mg RPC1063 (1 x 0.25 mg capsule)	0.5 mg RPC1063 (2 x 0.25 mg capsules)	0.5 mg RPC1063 (1 x 0.5 capsule) + Placebo IM injection				
RPC1063 1 mg	IM injection  0.25 mg RPC1063  (1 x 0.25 mg  capsule)  +  Placebo  IM injection	0.25 mg RPC1063 (1 x 0.25 mg capsule)	0.5 mg RPC1063 (2 x 0.25 mg capsules)	1 mg RPC1063 (1 x 1 mg capsule) + Placebo IM injection				
IFN β-1a 30 μg	IFN β-1a 30 μg- IM injection + Placebo (1 capsule)	Placebo (1 capsule)	Placebo (2 capsules)	IFN β-1a 30 μg- IM injection + Placebo (1 capsule)				

\* From Day 8 on, patients will continue receiving weekly IM injections (IFN β-1a/ placebo) and daily capsules (RPC1063/placebo) according to the assigned treatment level

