On Day 1 of treatment, careful cardiac monitoring of the patients is required. The first dose of RPC1063 should be administered in a setting in which resources to appropriately manage symptomatic bradycardia are available. A member of the Investigator team should be available to monitor the patient for the 6 hours monitoring period and will need to report any abnormalities to the treating neurologist. Atropine or Epinephrine need to be readily available to the site personnel.

Additional observation should be instituted until the finding has resolved in the following situations:

- The heart rate 6 hours post-dose is < 45 bpm
- The heart rate 6 hours post-dose is at the lowest value post-dose (suggesting that the maximum PD effect on the heart may not have occurred)
- The ECG 6 hours post-dose shows new onset second degree or higher AV block
- The ECG 6 hours post-dose shows a prolonged QTcF interval (>450 msec males, >470 msec females).

Should post-dose symptomatic bradycardia occur, initiate appropriate management, begin continuous ECG monitoring, and continue observation until the symptoms have resolved.

Should a patient require pharmacologic intervention for symptomatic bradycardia, continuous overnight ECG monitoring in a medical facility should be instituted, and the first dose monitoring strategy should be repeated at Day 5 if any cardiac safety issues were observed on Day 1.

Refer to Guidelines for Monitoring Patients Taking Their First Dose in Section 10.2.1.1 for further details.

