## 13.5. Analysis Populations

The following analysis populations will be used in the statistical analysis:

Intent-to-Treat (ITT): The ITT population will consist of all randomized patients who received at least 1 dose of study medication, with treatment assignment designated according to randomized treatment.

In Parts A and B, the primary efficacy analysis will be carried out in the intent-to-treat population.

Per Protocol (PP): The PP population will consist of the subset of the ITT population that excludes those patients who have had a major protocol violation. These will be defined prospectively, in advance of data lock and primary analyses, in the final SAP, by the (aggregate results blinded) project statistician. Membership in the PP population will be determined prior to unblinding.

Safety: The Safety population will consist of all patients receiving any study treatment and safety analyses will be carried out on this population according to highest dose of RPC1063 (up to 1 mg) actually received.

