### 8.2. Study Treatments

For all patients in the study, initial study treatment will consist of a 7-day dose titration regimen. For patients randomized to receive active treatment with RPC1063, this regimen will consist of RPC1063 0.25 mg starting on Day 1 for 4 days, then RPC1063 0.5 mg starting on Day 5 for 3 days, followed by the assigned treatment level beginning on Day 8.

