#### **10.1.5.** Adverse Events Leading to Treatment Discontinuation

All AEs collected with an investigational product action taken as "Permanently discontinued" will be summarized in a table and presented in a listing.

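### Does grouping safety patients by the highest RPC1063 dose received misplace those who stop during the 7-day titration?

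*SAP*

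**What the plan says.** SAP 5.3.3 admits to the Safety population anyone who took at least one dose of study drug. It then assigns the column: "All patients in the Safety population will be analyzed according to the highest dose of RPC1063 treatment actually received (up to 1 mg"). The sentence closes with a clause that limits the rule to patients whose treatment received and treatment assigned conflict: "and not according to the treatment they are randomized to receive, in the event there is a discrepancy". Protocol 13.5 gives the same rule more briefly, "according to highest dose of RPC1063 (up to 1 mg) actually received", without the clause on discrepancy.

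SAP 8.2 describes the titration of the RPC1063 arms: "RPC1063 0.25 mg starting on Day 1 for 4 days, then RPC1063 0.5 mg starting on Day 5 for 3 days". Protocol 9.5.1 (Part B) adds: "All patients will be dosed with their assigned RPC1063 treatment level beginning on Day 8". Protocol Table 7, headed "Titration Schedule for the RPC1063 Treatment Groups in Part B", sets the titration doses out in rows labelled by assigned treatment, so 0.25 mg and 0.5 mg stand in the row for RPC1063 1 mg.

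SAP 4.1 defines three regimens: interferon, RPC1063 0.5 mg and RPC1063 1 mg. There is no 0.25 mg group. Neither document defines a discrepancy or mentions titration in the grouping rule.

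**The concern.** In the first week the dose taken and the dose assigned are different numbers for every 1 mg patient, and in the first four days for every 0.5 mg patient as well. A rule worded by highest dose received, with no exemption for titration, could be programmed as the maximum of the dosing record. The 1 mg column would then hold only patients who reached Day 8, which is a selection on early tolerance made after randomisation.

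Three by-group summaries would be exposed:

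- The discontinuation table in SAP 10.1.5, which takes in "All AEs collected with an investigational product action taken as" permanently discontinued.
- Extent of exposure in SAP 8.2.1, where the 1 mg minimum would be 8 days by construction.
- Day 1 minimum heart rate in SAP 10.3.

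First-dose cardiac effects are a named special interest, and protocol 10.3.1 foresees trouble in this window: "the first dose monitoring strategy should be repeated at Day 5 if any cardiac safety issues were observed on Day 1". Day 5 is the first day at 0.5 mg. Losing early stops from the 1 mg column, while interferon keeps its own, would flatter the higher dose.

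**Working it through.** The plan states no figure on this point, so there is none to reproduce. The check is a mapping, a test of whether the literal rule can be applied at all, and a size under assumed rates.

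**1. Literal mapping** (highest dose up to the day of the last dose, from SAP 8.2 and protocol Table 7):

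| Last dose on | Randomised to 1 mg | Randomised to 0.5 mg |
|---|---|---|
| Days 1-4 | 0.25 mg, no dose column | 0.25 mg, no dose column |
| Days 5-7 | 0.5 mg column | 0.5 mg column |
| Day 8 or later | 1 mg column | 0.5 mg column |

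**2. Can the literal rule be applied?** An interferon patient has no RPC1063 dose, so the rule alone gives that patient no group. This removes about 400 of 1200 patients from every safety table. To produce the planned tables, the analyst has to begin from the randomised arm and reassign only where treatment received and treatment assigned conflict. That is what the SAP's final clause says. SAP 5.3.1 has the matching construction for the ITT population: analysis by randomised treatment where treatment received differs from it.

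**3. Is a titration stop a conflict?** Table 7 lists 0.25 mg and 0.5 mg under the assigned treatment of 1 mg, and SAP 8.2 describes the titration as the initial study treatment of every patient. A 1 mg patient whose last dose is on Day 6 has taken the assigned regimen and stopped it early. The patient stays in the 1 mg column, and nothing in the tables moves.

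**4. Size if the rule were nevertheless programmed literally.** The planned arm size is about 400 (SAP 5.1). The documents give no stopping rate for the titration week, so the counts are assumed: s stops per arm before Day 8, of which k fall on Days 5-7, the same in each arm.

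- 1 mg column: 0/(400 − s). Interferon: s/400. The understatement is s/400, which is 0.25, 0.5, 1.0 or 2.0 percentage points for s = 1, 2, 4 or 8.
- 0.5 mg column: 2k/(400 − s + 2k). Patients without a dose column: 2(s − k).
- For s = 4, where the true difference between the active arms is 0:

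| k | 0.5 mg column | 1 mg column | Spurious difference (points) | No dose column |
|---|---|---|---|---|
| 0 | 0/396 | 0/396 | 0 | 8 |
| 1 | 2/398 | 0/396 | 0.50 | 6 |
| 2 | 4/400 | 0/396 | 1.00 | 4 |
| 4 | 8/404 | 0/396 | 1.98 | 0 |

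As a further illustration, take 4 discontinuations for adverse events before Day 8 and 8 later ones among 400 patients randomised to 1 mg. The rate is 12/400 = 3.0% by randomised arm and 8/396 = 2.0% in the literal 1 mg column.

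The chance that at least one 1 mg patient stops in titration is 1 − (1 − p)^400. For assumed p of 0.1%, 0.25%, 0.5%, 1% and 2% it is 33%, 63%, 87%, 98% and over 99.9%. These values show that such a patient may well exist. They say nothing about which reading of the rule would be used.

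**The case for a change.** The strongest case for a change is that the text leaves the choice to a programmer. Protocol 9.5.6 makes no provision for dose adjustment, so titration is the only planned change of RPC1063 dose within a patient, and a rule worded by highest dose bears directly on it. The protocol's version lacks the discrepancy clause. Protocol 9.5.6 also requires patients who cannot tolerate the drug to be withdrawn, so a stop in the first week is foreseeable. The total RPC1063 group is named for medications and adverse events, but SAP 10.3 names no pooled column for vital signs. One sentence would settle the matter.

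Part of this stands: the documents do not define a discrepancy or mention titration in the grouping rule. It does not make the plan defective. The SAP exists to expand on the protocol (protocol 13.3), and it supplies the qualifier that the protocol omits. The wording by highest dose has an evident use, which is to place a patient who took capsules of both strengths. The cardiac route is also thin. Protocol 10.3.1 provides for repeat monitoring and does not call for stopping. Protocol 7.2.4 reports negligible further heart-rate reduction after Day 4 of the Phase 1 titration. On Day 1 both active arms take the same 0.25 mg, so a contrast between dose columns in that heart-rate table carries no dose information.

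**Conclusion.** No change to the plan is needed. The missing detail is how titration doses count in the safety grouping, and the documents point analysts to one workable answer: titration belongs to the assigned regimen, and a patient who stops before Day 8 stays in the randomised arm's column. Under that answer the effect on every table is zero.

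This rests on analysts starting from the randomised arm, as the SAP's discrepancy clause and the existence of the interferon arm require. If they did not, the effect would be about 0.25 to 2 percentage points in by-group descriptive summaries, for an assumed 1 to 8 stops per arm; the true number is unknown and probably small. Even then, the adverse events of patients who continue to Day 8 stay in their own column, and the total RPC1063 group keeps every patient. Discontinuation events, dosing dates and extended Day 1 monitoring are also listed by patient. SAP 10 tests no safety hypothesis, and efficacy is analysed by randomised arm. Writing the intent into the programming specifications would be harmless, but no conclusion of the trial depends on it.

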## 5.4. Other Important Considerations

#### 5.4.1. Definition of Baseline

Baseline data are defined as data collected which are prior to and/or on the date of first dose, usually also the same day as the Day 1 visit. If there is more than one value on or before Day 1, the value closest to and prior to (including on) the date of first dose will be used as the Baseline value.

#### **5.4.2.** Study Day Calculation for Reporting Purposes

The following conventions will be used to calculate study day for reporting purposes:

- Study Day = date of measurement first dose date +1, if date of measurement is on or after the first dose date.
- Study Day = date of measurement first dose date, if date of measurement is prior to the first dose date.

• Day 1 is the first dose date, no Day 0 is defined for this study.

#### 5.4.3. Visit Windows

A visit window method will be applied to determine visits across the study for MRI efficacy parameters and for the minimum times to confirmation of disability progressions. For MRI parameters, if a patient has multiple assessments within a visit window the value closest to the target day for that visit will be selected. If there are two values which are equidistant in terms of time then the later value will be selected. For disability progressions, a minimum length of time since the start of the progression is defined, based on the low end of the MRI visit window specifications.

The following visit windows are defined for MRI parameters:

Visit	Target Day	Window
Month 6	180	166 - 194
Month 12	360	346 - 374
Month 18	540	526 – 554
Month 24	720	706 - 734

The following minimum times are defined for disability progression confirmations:

- 3 month confirmation:  $\geq$  76 days after start of progression
- 6 month confirmation: ≥ 166 days after start of progression

For all efficacy and safety parameters, the last available assessment will be derived as the last value on treatment, whether scheduled or unscheduled.

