- 3 Patients will continue in the optional Blinded Extension period at least until the last patient reaches Week 72 and may continue on blinded therapy until a long-term safety study is available. For patients who continue in the Blinded Extension period beyond the nominal Week 72 visit, the assessments indicated will be repeated at 12-week intervals (with the exception of MRI which will be repeated annually). The End of Study visit will be performed 12 weeks after the previous scheduled visit and after all active patients have received at least 48 weeks of treatment in the Blinded Extension.
- 4 The Unscheduled Relapse Assessment Visit will be conducted in case of a suspected of possible relapse (see Section 9.1.2.3). After the Unscheduled Relapse Assessment Visit, patients should return to their usual visit schedule.
- 5 Patients who prematurely discontinue study treatment will be asked to complete an Early Termination visit.
- 6 Laboratory tests include Hematology, Chemistry, and Urinalysis
- 7 Urine beta hCG at each visit. If the urine pregnancy test is positive, do not dose and confirm with a serum pregnancy test.
- 8 For patients continuing to the blinded extension, MRI scans will be performed at approximately Weeks 48 and 72, and annually after Week 72. End of Study visit will include an MRI if it corresponds with this schedule.
- 9 Pulmonary function tests will include FEV1 and FVC measurements at all the above indicated visits. In addition, DLCO will be assessed at the Early Termination visit if the patient prematurely discontinues the study. If any abnormalities occur, they will be followed until such time as resolution is confirmed or no further improvement is expected by the investigator (based on a follow-up period of not less than 3 months).
- 10 If abnormal OCT findings, or visual signs or symptoms of macular edema are observed, a general ophthalmologic examination including eye history, visual acuity, and dilated ophthalmoscopy will also be performed.
- 11 An additional PK sample will be obtained for patients with any AE resulting in unblinding, discontinuation, or SAE.

Table 3 Schedule of Assessments – Part B: Screening, Baseline, and Treatment Period Visits

	Screening	Baseline	line Active-Comparator Treatment Period								
Visit	J	V1	V2	V3	V4	V5	V6	V7	V8	V9	V10
	M -1			M3	M6	M9	M12	M15	M18	M21	M24
Month		M1	M1	(W13)	(W26)	(W39)	(W52)	(W65)	(W78)	(W91)	(W104)
Study Day	-30 to -1	1	15	92	183	274	365	456	547	638	729

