# 10.5. Early Termination Visit

Patients who prematurely discontinue study treatment will be asked to complete an early termination visit. The following assessments will be performed:

- Blood/urine sampling for the following laboratory tests:
  - Hematology: RBC count, total and differential WBC count (basophils, eosinophils, lymphocytes, monocytes, and neutrophils), platelet count, hemoglobin, hematocrit, MCV, MCH, and MCHC
     Note: All total WBC and differential WBC counts will be blinded during the study.
  - Blood chemistry: sodium, potassium, chloride, calcium, magnesium, phosphate, blood urea nitrogen, random glucose, albumin, alkaline phosphatase, creatinine, SGPT/ALT, SGOT/AST, GGT, amylase, total bilirubin, conjugated bilirubin, hemoglobin A1c. Abnormal laboratory parameters inconsistent with clinical presentation of MS or suspicious of underlying medical condition should be repeated for accuracy. If an increase of amylase above the clinically notable value (≥ 300 U/L) is observed at any post randomization visit, lipase should be tested to determine the origin of elevated amylase (pancreatic versus extra pancreatic)
  - Urinalysis: leukocytes, specific gravity, bilirubin, blood, glucose, ketones, pH, protein, and urobilinogen
  - Urine beta-hCG (females of childbearing potential only). If the urine pregnancy test is positive, do not dose and confirm with a serum pregnancy test.
  - Coagulation panel: PT and partial thromboplastin time PTT
  - sTSH

- PK sampling
- Complete physical examination: including evaluation of heart, lung, head and neck, abdominal, neurological, skin, and extremities
- Weight
- Vital signs: body temperature, blood pressure and heart rate
- 12-lead ECG
- Review study drug accountability and compliance
- Brain MRI
- EDSS and neurological examination
- MSFC and LCLA
- MSQOL-54
- Pulmonary function tests including FEV1, FVC, and DLCO measurements
- OCT evaluation
- Dermatological examination
- Suicidality assessment using the C-SSRS
- Record concomitant therapy
- Record AEs/SAEs

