## 11.1. Efficacy Assessments

#### 11.1.1. Magnetic Resonance Imaging (MRI)

Brain MRIs will be acquired with and without Gadolinium. The same MRI protocol will be used across all sites. To ensure quality data and standardization the same machine and software should be used throughout the study. MRIs for MS lesions will be read blinded to treatment allocation at a centralized reading facility.

In Part B and in the Blinded Extension to Part A, MRI scans should not be performed until 30 days after the last dose of methylprednisolone treatment for relapse. Previously scheduled MRIs should be rescheduled as necessary if a relapse occurs.

Total number of GdE lesions, number of new or enlarging hyperintense T2-weighted lesions, lesion volume (T2-weighted images), volume of unenhancing T1-weighted lesions and brain volume (i.e., brain atrophy) will be collected and reported.

The MRI scans will be read locally for non-MS pathology.

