### 9.3.1. Analysis

Secondary Endpoints: The proportion of patients who are GdE lesion-free at Month 24, and the proportion of patients who are T2 lesion-free at Month 24

Each of these endpoints will be analyzed using a Cochran-Mantel-Haenszel (CMH) test

stratified by region and EDSS category at Baseline. The numbers and percentages of patients with 0, 1-2, 3-4, and  $\geq$  5 lesions will be reported. The proportion of patients who are lesion-free will be reported along with the associated 95% CI. The difference in proportions between each RPC1063 group and the IFN  $\beta$ -1a group will also be reported with the associated 95% CI and CMH p-value. Patients who are missing the Month 24 MRI data will be considered non-responders, i.e., as not being lesion-free.

Sensitivity analyses will be conducted using the LOCF method for replacing missing Month 24 MRI data and on the subset of patients with non-missing Month 24 MRI data (observed cases analysis).

Secondary Endpoint: Change in normalized brain volume (atrophy) on MRI scans from Baseline to Month 24

Brain volumes will be reported in cm^3. If the data are collected in mm^3, then a transformation will be applied by dividing the result in mm^3 by 1000 to convert to cm^3 prior to analysis.

Actual brain volumes, change from Baseline to each visit, and percent change from Baseline to each visit will be summarized. Comparisons of the change and percent changes between the treatment groups will be analyzed using an analysis of covariance (ANCOVA) model adjusted for region, EDSS category at Baseline, and brain volume at Baseline. The mean difference between each RPC1063 treatment group and IFN  $\beta$ -1a will be reported with the associated 95% CI and p-value. Patients with missing data will have their results imputed via LOCF.

Secondary Endpoint: Change in MSFC score from Baseline to Month 24 (including the low-contrast letter acuity test [LCLA] measurement of visual function as a component)

The MSFC score is a battery of the following 3 individual scales:

- The Timed 25-Foot Walk is a quantitative measure of lower extremity function
- The 9-Hole Peg Test is a quantitative measure of upper extremity (arm and hand) function
- The Symbol Digit Modalities Test (SDMT) is a measure of cognitive impairment that assesses attention, visuoperceptual processing, working memory, and psychomotor speed

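### The SAP's MRI visit windows do not match the Part B scan schedule: most scans deferred for relapse steroids fall in no window, and their handling is not defined

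*SAP*

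**What the plan says.** - **Windows.** SAP 5.4.3: "A visit window method will be applied to determine visits across the study for MRI efficacy parameters". The two rows that matter read "Month 12 360 346 - 374" and "Month 24 720 706 - 734" (visit, target day, window). There are also rows for Month 6 (166–194) and Month 18 (526–554).
- **Schedule.** The study-day row of protocol Table 3, from Month 12 to Month 24, reads "365 456 547 638 729", each ±5 days. Brain MRI is marked only at screening, Month 12 and Month 24.
- **Deferral.** Protocol 11.1.1: "MRI scans should not be performed until 30 days after the last dose of methylprednisolone treatment for relapse", followed by "Previously scheduled MRIs should be rescheduled as necessary if a relapse occurs". No latest date is given.
- **Extension rule.** Protocol section 10 lets visit windows be stretched case by case for scheduling reasons, but lists brain MRI as an exception.
- **Early termination.** Protocol 10.5: "Patients who prematurely discontinue study treatment will be asked to complete an early termination visit". The procedures at that visit include brain MRI.
- **Use of the scans.** In SAP 9.2.1 the T2 and GdE key secondary models both use the log of the number of available scans as offset, without defining which scans are available. For the lesion-free endpoints, SAP 9.3.1 says: "Patients who are missing the Month 24 MRI data will be considered non-responders".

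**The concern.** The SAP targets are multiples of 30 days and do not follow the trial's own visit days. All the slack they add at Month 24 is on the early side, while the one protocol rule that systematically moves a scan moves it later. On the natural reading, a scan that falls in no window belongs to no visit.

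A patient whose Month 24 scan was postponed as the protocol directs would then count as not lesion-free, and would lose a scan from the T2 and GdE counts. Those two counts are the first two ranked key secondary endpoints. Deferral follows relapse, and early-termination scans follow stopping treatment, so which scans fall outside a window is not random.

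A patient with no windowed post-baseline scan at all would have an offset of log(0) and could not enter the T2 model.

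**Working it through.** **1. The SAP windows reproduced.** 30 × month ± 14 gives 166–194, 346–374, 526–554 and 706–734, all four rows exactly.

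**2. Against the protocol visits.**

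| | Month 12 | Month 24 |
|---|---|---|
| SAP target | 360 | 720 |
| Protocol day | 365 | 729 |
| Target early by | 5 days | 9 days |
| Protocol ±5 window | 360–370 | 724–734 |
| SAP room before it | 360 − 346 = 14 | 724 − 706 = 18 |
| SAP room after it | 374 − 370 = 4 | 734 − 734 = 0 |

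Each 29-day SAP window contains the whole 11-day visit window, so no on-time scan is lost.

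**3. Steroid deferral.** Let S be the planned scan day and L the day of the last steroid dose, with L ≤ S. The scan is deferred if L + 30 > S, which gives 30 possible days (S − 29 to S). Done at the earliest permitted day, it misses the window if L + 30 is past the upper edge.

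- Month 24 (edge 734): missed if L ≥ 705. With S = 729, L = 705–729: **25 of 30**. With S = 724, 20 of 30; with S = 734, 30 of 30.
- Month 12 (edge 374): missed if L ≥ 345. With S = 365, L = 345–365: **21 of 30**. With S = 360, 16 of 30; with S = 370, 26 of 30.

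**4. Size at Month 24.** Share of patients ≈ ARR × days / 365.25, with every relapse steroid-treated and relapses spread evenly. The ARRs are the planning values: 0.30 for IFN (both documents), and for RPC1063 0.17 (SAP 5.1) and 0.19 (protocol 13.2).

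| Days at risk | IFN 0.30 | RPC1063 0.19 | RPC1063 0.17 |
|---|---|---|---|
| 20 (S = 724) | 1.6% | 1.0% | 0.9% |
| 25 (S = 729) | 2.1% | 1.3% | 1.2% |
| 30 (S = 734) | 2.5% | 1.6% | 1.4% |

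At the nominal day this is about 8 of 400 IFN patients and about 5 of 400 per RPC1063 arm. At Month 12 (21 days) it is about 7 against 4 of 400.

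**5. Early termination.** Assume dropout uniform over Days 15–723 (709 days) and a scan for every dropout.

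- Days inside a window: 29 + 29 + 29 + 18 (706–723) = 105. Outside: 604/709 = 85.2%.
- Share of all patients: 0.852 × 12% (SAP 5.1) = 10.2%; 0.852 × 17% (protocol 13.2) = 14.5%.
- No windowed post-baseline scan: Days 15–345 are 331 days, less the 29 of the Month 6 window, so 302. 302/709 = 42.6%, which is 5.1% of patients at 12% dropout and 7.2% at 17%, or about 20 to 29 per arm of 400.

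Dropout concentrated earlier (exponential hazard 0.17 to 2 per year, over Days 1–723) puts 86–91% outside.

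**The case against.** **The SAP never says an out-of-window scan is discarded.** A reader might infer that collected data will be thrown away, but the text does not support that as a stated rule. Section 5.4.3 also derives a last available assessment from scheduled or unscheduled values, the offset refers to available scans, and the sensitivity analyses include carrying post-baseline scans forward. This stands: the defect is an unstated rule. These provisions do not settle it either. The last available assessment is limited to values on treatment, and early-termination scans, and possibly deferred Month 24 scans, come after the last dose. The main T2, GdE and lesion-free analyses do not invoke it. For those endpoints carrying forward is only a sensitivity analysis, and whether an unwindowed scan qualifies is not said.

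**The windows are not narrow against the schedule.** This stands. They fail only for deferred and early-termination scans.

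**The early-termination share is not caused by centring or width.** This stands. Even ±45 days around Days 365 and 729 covers only 91 (320–410) + 40 (684–723) = 131 of 709 days, so 82% would still fall outside, against 85% now. A scan months before Month 24 is also rightly not a Month 24 GdE or lesion-free value. What remains is its place in the T2 analysis.

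**The sizes are upper figures.** This stands. Patients may, not must, receive steroids for a relapse (protocol 9.1.2.3). Dropouts are only asked to attend the termination visit, and some are lost or withdraw consent.

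**The two protocol rules can be read together,** the bar on extension as a general scheduling rule and the steroid deferral as a specific exception. That reading is reasonable, but the protocol does not state it.

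**Conclusion.** The mismatch is a fact of the documents: targets 5 and 9 days early, no late room at Month 24, and two windows without a scheduled scan. On the natural but unstated reading that a scan in no window has no visit, most steroid-deferred scans miss theirs.

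The relapse-linked loss at Month 24 is small: about 1.6–2.5% on IFN and 0.9–1.6% on RPC1063, if all relapses are treated and deferred scans are done at the earliest permitted day. The early-termination part is larger: at most 10.2–14.5% of patients have an unwindowed termination scan, and 5.1–7.2% have no windowed post-baseline scan for the T2 model. It rests on uniform dropout and a scan for every dropout.

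A reader might infer that the loss favours RPC1063, because relapses are expected more often on IFN. The documents do not support a net direction. Scoring these patients as not lesion-free would count more against IFN, while losing relapsing patients' scans from the count models would tend to work against RPC1063. The lesion-free endpoints are also outside the multiplicity-controlled ranking. The point is a specification gap in two ranked endpoints, worth closing before unblinding.

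**What to change.** In SAP 5.4.3:

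- Set the targets to Day 365 and Day 729, and extend the late edge to 35 days after nominal: Day 400 and Day 764. Every deferral counted above then falls inside, because the latest is 734 + 30 = 764. Re-centring alone with ±14 days would still miss 16 of 30 for a nominal-day plan.
- Remove the Month 6 and Month 18 windows, or say what they are for.

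In SAP 9.2.1 and 9.3.1:

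- Define which scans count as available.
- State that early-termination scans outside the windows count in the T2 analysis, with the offset counted to match, but are not Month 24 values for GdE or lesion-free status.
- Add a sensitivity analysis that excludes Month 24 scans done after the last dose.

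In the protocol, reconcile section 10 (MRI windows not stretched for scheduling) with 11.1.1 (MRI rescheduled after relapse steroids).

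The cost is wording only. Scan timing will be slightly more spread, and some Month 24 scans will be off treatment, which the added sensitivity analysis addresses.
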